## **RISK/BENEFIT ASSESSMENT**

This study poses minimal risk to participants. Nevertheless, there may be a small risk related to a breach of confidentiality and psychological distress related to topics discussed during the interviews. Further, children will be recruited in this study requiring special precautions to minimize potential additional risks for vulnerable populations. There will be no direct benefit to the adolescents and parents participating in this study. However, findings from this study may inform programs and interventions to reduce multi-level determinants influencing HPV vaccine completion among adolescents.

**Risks:** To mitigate the potential risk for psychological distress related to discussion about cancer, sexual health, and the HPV vaccine, participants will be provided their rights to refuse answering questions during interviews that make them feel uncomfortable and withdraw from the study at any time as specified in the informed consent and child assent. Further, interviews will be scheduled at times convenient with participants' schedule (as specified by parents and adolescents) and at a private location of their preference (i.e. reserved room at Duke University campus or local library, home, etc.) to promote schedule flexibility and to make participants feel at ease during interviews. To minimize risks to children, assent will be obtained from each child which will describe their rights to participate in the study and refuse to answer questions that make them feel uncomfortable. The child's confidentiality will also be maintained through separate individual interviews away from their parents. The interviewer will promote open and honest communication with each participant to create a trusting environment. To protect confidentiality and prevent against a potential breach, each subjects' charts will be provided a participant ID number. Names and date of birth will not be recorded on data collection forms or used in qualitative interviews. All electronic data will be stored in a password protected share drive in which only study personnel will have access to. All hard copy forms (i.e. informed consent, child assent, and demographic surveys) will be stored in a locked file cabinet at DUSON. For aim 1, EHR data containing protected health information (i.e. addresses, zip codes, and date of vaccine administration) will be imported and stored in a secure folder in PACE and later removed from the dataset once area deprivation values and the number of miles from participants' place of residence to the selected pediatric clinic have been determined, and the date of vaccine administration has been converted to months. For aim 2, protected health information obtained for recruitment (e.g. names, addresses, phone numbers, and email addresses) will be recorded on a password-protected Excel document that will be stored in a secure folder within the study's shared drive and destroyed at the completion of data analysis. All collected information will be stored in a database on a standalone database server hosted by Duke Health Technology Services (DHTS). The database server resides behind the DHTS internal firewall and access to the server is controlled via firewall rules. All collected data is

backed up daily, both on the local server and by the DHTS enterprise backup system. The PACE network and secure folder on the shared drive for this study will be housed within this server. Only members of the study team will have access to this folder and PACE network.

**Benefits:** This study presents a minimal risk to participants. While there are no anticipated benefits to participants from being in this study, the benefits to society by helping to reduce barriers to HPV vaccine completion among adolescents outweigh the risks to individuals.

## **COSTS TO THE SUBJECT**

There are no direct costs to the participants of the study.

## **DATA ANALYSIS & STATISTICAL PLAN**

**Aim 1:** Descriptive statistics will be used to detail the characteristics and key measures for the eligible adolescents and their parents. Logistic regression will be used to determine the role that social determinants play in predicting HPV vaccine completion within 14 months. Individual-level determinants will be adolescent's age, sex, race/ethnicity, and insurance type; community-level determinants will be area deprivation index for residence and distance from clinic. Power calculations indicated a required sample size of 600 charts for adolescents who received the first dose of the HPV vaccine to achieve 80% power when conducting the primary analysis using multivariable logistic regression and supplemental regression analysis using Cox proportional regression models. This sample size estimate was based on the following assumptions: (a) up to 10 predictor terms in the final model; (b) medium effects, indicated by adjusted odds or hazards ratios; (c) two-tailed tests with significance set at 0.05 per test; and (d) an overall missing rate of less than 5% for terms in the model after imputation when needed. However, all charts that meet the eligibility criteria will be analyzed and it is estimated that the sample size will exceed the required sample size of 600 charts.

**Aim 2:** Directed qualitative content analysis will be conducted to examine parents and adolescents' experience with the HPV vaccine and barriers and facilitators to completing the vaccine series across level of determinant (e.g. individual, relationship, and community). For data integration, quantitative and qualitative data will be analyzed separately initially. Then, results from each separate analysis will be presented in data displays with an integrative summary for each level of determinant to assess patterns between quantitative and qualitative data and provide further description of the role that social determinants play on HPV vaccine completion.

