### PURPOSE OF THE STUDY AND HYPOTHESES TO BE TESTED

The purpose of this study is to identify individual-, relationship-, and community-level determinants of HPV vaccine completion among adolescents ages 11 to 14 who received one dose of the vaccine, and barriers and facilitators to completion as described by parents and adolescents. The following hypothesis will be tested for Aim 1:

**H1:** Younger adolescents, boys, racial/ethnic minorities, adolescents without health insurance and those living in areas with high deprivation and far distances from the clinic will be less likely to complete the HPV vaccine series.

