### BACKGROUND & SIGNIFICANCE

The human papillomavirus (HPV) is the most prevalent sexually transmitted infection in the U.S. and causes nearly 90% of cervical and anal cancers and 70% of vaginal, vulvar, penile and oral cancers (Centers for Disease Control and Prevention (CDC), 2016; Gillison, Chaturvedi, & Lowy, 2008; Reiter et al., 2013). The HPV vaccine, Gardasil 9, is recommended for administration to adolescents before engaging in sexual activity to prevent exposure against nine commonly transmitted strands. Despite the efficacy of the vaccine in preventing HPV and associated cancers, HPV vaccine rates remain low, with initiation rates (i.e. receive 1 dose) at 65% among adolescent girls and 56% among adolescent boys. Completion rates (i.e. receive 2 or 3 doses depending on certain age groups) are significantly lower at 49.5% and 37.5% among adolescent girls and boys respectively (CDC, 2017; Walker et al., 2016).

Recently, the Advisory Committee on Immunization Practices (ACIP) lowered the number of required doses for adolescents (ages 11 to 14 years) to 2 doses based on evidence demonstrating sustained immunogenicity after the second dose (Meites, Kempe, & Markowitz, 2016). However, since these changes occurred in late 2016 (Walker et al., 2016), current completion rates do not reflect vaccine completion solely for this age group (Meites et al., 2016). Further, the vaccine remains on a 6 to 12-month administration schedule, requiring adolescents to return to clinics to receive subsequent doses (Meites et al., 2016). Given the gap between vaccine initiation and completion rates it is believed that disparities in HPV vaccination might be exacerbated due to social determinants. To date, most of the literature on HPV vaccination in adolescence has largely focused on individual-level determinants influencing parents to refuse vaccination and initiate the vaccine series, including parents' beliefs, attitudes, awareness (Tsui

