## **SUBJECT RECRUITMENT AND COMPENSATION**

Recruitment will occur in-person at Duke University Primary Care Pediatrics at Roxboro Road, by phone, email or mail. Sixteen adolescents and 16 parents will be recruited from the clinic (n=32 participants). This clinic was carefully chosen for their diverse patient population of adolescents (26.4% White, 40.9% Black, 20.5% Hispanic, 2.8% Asian, and 16.7% Other). I will track race/ethnicity and gender of potential subjects to ensure participant selection is representative across all demographic groups. A request for waiver of informed consent will be submitted to the IRB to access previously collected data on adolescents' charts and the NCIR database retrospectively for Aim 1. For Aim 2, a request for waiver of informed consent will be submitted to the IRB to use adolescents' charts and the NCIR database to identify potential eligible subjects through chart reviews and to make initial contact with eligible subjects for study participation by the healthcare provider prior to obtaining consent from parents and assent from adolescents. I have gained permission to conduct chart reviews and access to use the NCIR

database to prescreen for eligible participants prior to their scheduled clinic visit. Prior to the start of the clinic day, I will provide a list of eligible participants to each healthcare provider. Clinic healthcare providers have agreed (letters of support) to provide a brief introduction of the study during clinic visits, by phone, email, and through letters sent via mail. Initial contact with eligible parents and adolescents will occur after the study has been introduced and participants have expressed their interest in the study to the healthcare provider. A brochure will be given to healthcare providers and eligible participants to provide them with additional information about the study.

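### Does the 80% power claimed for 600 charts fail for the minority-group and uninsured contrasts in H1?

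*Combined protocol and SAP*

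**What the plan says.** The Aim 1 paragraph of DATA ANALYSIS & STATISTICAL PLAN gives one sample size, a "required sample size of 600 charts for adolescents who received the first dose of the HPV vaccine to achieve 80% power", for two models: the primary logistic regression and a supplemental Cox regression. The assumptions are at most ten model terms, "medium effects, indicated by adjusted odds or hazards ratios", "two-tailed tests with significance set at 0.05 per test", and less than 5% missing after imputation. The same paragraph adds that all eligible charts will be analysed and that their number should exceed 600.

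The hypothesis in PURPOSE OF THE STUDY AND HYPOTHESES TO BE TESTED expects lower completion among several groups, including "racial/ethnic minorities, adolescents without health insurance and those living in areas with high deprivation". Neither MEASURES nor the analysis section lists race/ethnicity categories, a reference group or insurance categories. The clinic's mix, "26.4% White, 40.9% Black, 20.5% Hispanic, 2.8% Asian, and 16.7% Other", appears in SUBJECT RECRUITMENT AND COMPENSATION to explain why the clinic was chosen.

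**The concern.** The power of a test on an indicator variable depends on how many people fall in each group. The plan gives one power at one sample size for every term, although H1 concerns groups of very different size. By the clinic's mix, 600 charts would hold about 158 White, 245 Black, 123 Hispanic, 100 Other and 17 Asian adolescents. If 600 is just enough for an evenly split predictor, it is too few for the rest. In a study of disparities, a non-significant result for a minority or uninsured group could then be read as an adequately powered null.

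**Working it through.** **Inputs.** From the plan: N = 600, two-sided 0.05, 80% power, and the clinic shares. The shares sum to 26.4 + 40.9 + 20.5 + 2.8 + 16.7 = 107.3%, so they were used both as printed and rescaled to 100%. The plan gives no completion rate for the power calculation. BACKGROUND & SIGNIFICANCE says completion rates "are significantly lower at 49.5% and 37.5% among adolescent girls and boys respectively" (mean about 44%). Divided by its initiation rates of 65% and 56%, these become 76.2% and 67.0% (mean about 72%). The range used is therefore 44–72%. Assumed, because the documents are silent: odds ratios of 1.65 to 2.5, and uninsured shares of 5% and 10%.

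**The plan's own figure.** 600 cannot be reproduced, because no odds ratio is stated. Working backwards, an evenly split predictor with 600 charts has 80% power at an odds ratio of 1.58–1.66 unadjusted. With an assumed R² of 0.2 among predictors, a two-proportion calculation gives 1.68–1.76.

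**Formula (unadjusted Wald test).** With group sizes n1 and n0 and completion p:

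- SE = √[(1/n1 + 1/n0) / (p(1 − p))]
- detectable OR = exp[(1.960 + 0.842) × SE]
- power = Φ(ln OR / SE − 1.960)

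Example, Black versus White, printed shares, p = 0.50: SE = √[(1/245.4 + 1/158.4)/0.25] = 0.204, and the detectable OR is exp(2.802 × 0.204) = 1.77.

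**Results at 600 charts** (range over p = 0.44–0.72; for the four contrasts of single groups with White, also over both versions of the shares):

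| Contrast | OR detectable at 80% | Power, OR 1.65 | Power, OR 2.0 | Power, OR 2.5 |
|---|---|---|---|---|
| Evenly split predictor | 1.58–1.66 | 79–87% | 97–99% | over 99% |
| All minorities (73.6%) vs White | 1.68–1.78 | 68–77% | 92–96% | 99% or more |
| Black vs White | 1.77–1.93 | 57–69% | 84–93% | 97–99% |
| Hispanic vs White | 1.96–2.17 | 44–55% | 71–82% | 91–97% |
| Other vs White | 2.04–2.28 | 40–50% | 65–78% | 88–95% |
| Uninsured, 10% assumed | 2.14–2.34 | 38–45% | 63–72% | 86–92% |
| Uninsured, 5% assumed | 2.86–3.22 | 22–27% | 38–46% | 59–69% |
| Asian vs White | 4.2–5.3 | 13–16% | 22–27% | 34–43% |

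The verdict on each row turns on the odds ratio chosen. Taking 1.65 because it is what 600 charts support for an even split, and then finding that uneven splits fall short, is circular. At 2.5 every row passes except the last two.

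**Coding.** Ten terms can come from age 1, sex 1, race/ethnicity 4, insurance 2, deprivation 1 and distance 1. They can equally come from race/ethnicity 3, insurance 3 and four single terms. Ten is also a ceiling. The count therefore does not establish a separate Asian indicator, and H1 names minorities collectively.

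**Sex.** The rates among initiators give an odds ratio of (0.762/0.238)/(0.670/0.330) = 1.58. Power is 70% with 300 per sex and 68% with 285. The rates as printed, 49.5% versus 37.5%, give 1.63 and power of 84% and 83%. The result depends on the conversion. The Background itself warns that current rates do not describe this age group alone. An effect of 1.58 is also smaller than 1.65, so falling short there says little about medium effects.

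**Supplemental Cox model.** For a 20.5% group against all others at HR 1.5, the events needed are 2.802² / [0.205 × 0.795 × (ln 1.5)²] ≈ 293. With 44–71% of 600 completing (264–426 events), power is 76–92%.

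**The case for a change.** The strongest case for a change is that, if each clinic category becomes its own term, no odds ratio from 1.5 to 2.5 makes the sentence true throughout. At 2.5 the Asian contrast needs about 1,480–1,970 charts (p = 0.50 to 0.72), roughly 2.5 to 3.3 times the stated number, and the plan does not say how far the sample will exceed 600. The calculations above are also unadjusted, so correlation among predictors would lower every figure. Rewriting one paragraph costs almost nothing, and a disparities study should not invite a null to be over-read.

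Two parts of this stand. The power statement does not show the inputs that a reader would need to check it, and very small groups modelled alone would have far less than 80% power. The rest depends on a category coding and an insurance mix that the plan does not contain. A joint test of race/ethnicity, or merging a group of about 17 with Other, is a sensible choice for the analyst once the counts are known. It does not correct anything the plan has specified.

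**Conclusion.** No change to the plan follows. The claim is unverifiable as written, but it is not shown to be wrong. Unadjusted, at an odds ratio of 2.5 and completion of 44–72%, 600 charts give at least 86% power for an evenly split predictor such as sex, for Black, Hispanic and Other versus White, for all minorities versus White, and for a 10% uninsured group. At 1.65 only the evenly split predictor reaches about 80%. The shortfalls that persist at 2.5 are a separate Asian term and a 5% uninsured share. The plan specifies neither.

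The remaining gap is missing detail: the odds or hazard ratio, completion rate, group shares, coding and correlation behind 600. It has no effect on the results. The chart review is retrospective, takes every eligible chart and does not stop at 600, so a restated power paragraph would change no data, estimate or test. When results are reported, the observed group sizes and the interval around each odds ratio will show which contrasts were informative, more directly than a revised planning figure could.

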**Procedures: Aim 1.** A request for waiver of informed consent will be submitted to the IRB to access previously collected data on adolescents' charts retrospectively. The PI will collaborate with a research data manager to abstract eligible electronic health records through the Maestro Care database. Data pulled from the Maestro Care database will be imported and stored in a secure folder in PACE, a highly protected network space where users can analyze and work with identifiable protected health information. Data on adolescents' HPV vaccine completion will be recorded on data collection forms using the number of vaccine doses received, the date in which the vaccine doses were administered, and clinic location in which the vaccine doses were received. The North Carolina Immunization Registry (NCIR) will be used to verify HPV vaccine completion in the event that the adolescent receives any of the vaccine doses outside of the Duke University Health System (DUHS) network. The NCIR is a secure, web-based database where healthcare providers report immunizations administered to patients within North Carolina. I have gained view-only access to the NCIR through the selected pediatric clinic and will only use the database to record the number of HPV vaccine doses, the dates in which the doses were administered, and clinic location in which the doses were received for eligible adolescent charts for Aim 1. A cohort of adolescents will be created by examining charts of all adolescents ages 11 to 14 who received 1 dose of the HPV vaccine from January 2017 to December 2017. This cohort will be followed from January 2018 to February 2019 to assess vaccine completion within a 14-month period documented in the adolescents' electronic medical chart. Data from chart reviews will be partially de-identified; zip codes, addresses from participants and the person listed as the emergency contact, and the dates of HPV vaccine administration will be the only identifiable data recorded from the chart reviews. Zip codes will be recorded to determine

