the area deprivation index of the adolescent's place of residence. Addresses will be recorded to calculate the number of miles for the distance from clinic variable. Lastly, the date of HPV vaccine administration will be used to determine the number of months between receipt of the first and second dose within a 14-month period. However, once area deprivation index values have been determined, the distance from clinic miles calculated using geographic information systems (GIS) software, and the date of vaccine administration have been converted to months (e.g. 1st dose = 1 month; 2nd dose = 8 months from first dose) participants' zip codes, addresses, and date of vaccine administration will be deleted from the dataset. Each eligible adolescents' chart will be provided with a subject ID number. To minimize the risk of loss of confidentiality, all data will be stored and secured in the PACE network. Additional data (i.e. analyses results) will be stored in an electronic, password-protected share drive at Duke University School of Nursing and will be backed up daily. Only the study team will have access to both the share drive and PACE network.

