## MEASURES

Data collected will include (1) adolescent and parent demographic characteristics, (2) vaccine completion, and (3) parent and adolescent individual interviews.

**Demographic Characteristics (Aim 1).** The adolescent's age, sex, race/ethnicity, insurance type, area deprivation index for residence, and distance from clinic will be obtained from EHR data and recorded on data collection forms. Adolescent's insurance type will be determined by the parent's insurance provider listed in the chart. Area deprivation index for residence, determined by the parent household where the adolescent lives, will be measured using zip codes and linked by subject ID number with the area deprivation index public database to determine the index value for their place of residence. This index value is assigned to neighborhoods using 9-digit zip codes and identifies the percentage of the population that experiences socioeconomic deprivation within a neighborhood in a given geographic area based on the following variables: Education, median family income, employment, income disparity, housing units, federal poverty level, single-parent households, and household characteristics. Higher index values indicate higher levels of deprivation among a geographic area which has been associated with poorer health outcomes (University of Wisconsin Health Innovation Program, 2017). Distance from clinic will be calculated using the adolescent's address listed as the primary residence in their chart and measured as the number of miles from their place of residence to the pediatric clinic. The number of miles will be calculated using geographic information systems (GIS) software. All data will be used to describe the relationship between social determinants and vaccine completion. Parent or legal guardian characteristics including their age, sex, race/ethnicity, and relationship to the adolescent will also be collected to further describe the sample.

**Vaccine Completion (Aim 1).** Data on the number of HPV vaccine doses that the adolescent received within a 14-month period will be obtained from EHR data. In addition, the date of

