## **SELECTION OF SUBJECTS**

Subjects will be identified in person at the Primary Care Pediatrics at Roxboro Road. I have gained permission from the selected clinic to conduct chart reviews and use the NCIR database to prescreen for eligible participants prior to their scheduled clinic visit. Eligibility will include: Adolescents ages 11 to 14 years who have received 1 dose of the HPV vaccine series between January 2017 and December 2017; parents as defined as the adolescent's biological mother or father, step-parents, or legal guardian; and, parents or legal guardians who self-identified as the primary caregiver of the adolescent child and most likely to make medical decisions for the adolescent. Only one parent or legal guardian and one adolescent per household will be included in the individual interviews. Exclusion criteria includes: Parents and adolescents with cognitive impairment, adolescents emancipated from their parents or legal guardian, and pregnant adolescent girls will be excluded from this study. Pregnant girls will be excluded from the study because the vaccine is not recommended for use in this population (CDC, 2016). Further, adolescents who did not receive any doses of the series are excluded since the focus of this study is to understanding barriers and facilitators to HPV vaccine completion.

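### Aim 1 makes no allowance for siblings in the cohort; if there are any, standard errors for household-level determinants may be slightly too small (minor, cheap to fix before addresses are deleted)

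*Combined protocol and SAP*

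**What the plan says.** The Aim 1 cohort (DESIGN AND PROCEDURES, Procedures: Aim 1) is built by "examining charts of all adolescents ages 11 to 14 who received 1 dose of the HPV vaccine from January 2017 to December 2017". The DATA ANALYSIS & STATISTICAL PLAN section states that "all charts that meet the eligibility criteria will be analyzed", names a "primary analysis using multivariable logistic regression and supplemental regression analysis using Cox proportional regression models", and assumes "two-tailed tests with significance set at 0.05 per test". It mentions no cluster-robust variance, random effect, frailty term or other allowance for charts from one household, and it does not name a variance estimator.

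SELECTION OF SUBJECTS does contain a household rule: "Only one parent or legal guardian and one adolescent per household will be included in the individual interviews". By its own terms that rule is limited to Aim 2.

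MEASURES derives the deprivation index from the household where the adolescent lives and distance from the primary residence. On insurance it says: "Adolescent's insurance type will be determined by the parent's insurance provider listed in the chart".

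The Aim 1 procedures record "zip codes, addresses from participants and the person listed as the emergency contact". Once the index values, mileages and dose intervals have been derived, the participants' zip codes, "addresses, and date of vaccine administration will be deleted from the dataset".

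**The concern.** Two siblings can both be aged 11 to 14 and both have their qualifying dose in 2017, and nothing in the Aim 1 criteria removes one of them. Siblings at one address share the deprivation index and the distance exactly, and would usually share insurance. Their completion may also be alike for reasons that the model does not capture, such as the same parent making the decisions and the appointments. Ordinary logistic and Cox regression treat the two charts as independent. For a determinant that does not vary within the household, that overstates the information and understates the standard error.

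Insurance, deprivation and distance are all named in hypothesis H1, and each is tested at 0.05. At stake are slightly narrow intervals and a slightly raised false-positive rate for those terms. A larger sample does not remove the problem, because the proportional error depends on the sibling share and the correlation, not on the number of charts. Once addresses are deleted, the study could neither correct for siblings exactly nor show reliably that there are none.

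**Working it through.** **The plan's own figure.** The required 600 charts can be neither reproduced nor refuted, because the plan gives no numerical odds or hazard ratio, completion rate, exposure prevalence or covariate correlation. It is plausible. Comparing the Background's completion rates of 49.5% and 37.5% in two equal groups at 80% power and two-sided 0.05 needs 534 charts (568 with continuity correction). This point does not dispute the 600.

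**Inputs.** From the plan: 600 charts, two-sided 0.05 per test. Assumed, because the documents give neither: the share *f* of adolescents with a sibling in the cohort, 0-20%, and the residual within-household correlation *ρ* of completion, 0.3-0.7.

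**Formulae** (sibling pairs, determinant constant within the household). A chart with a sibling carries a variance factor 1 + ρ and a single chart a factor 1, so

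- design effect: DE = (1 − f) + f(1 + ρ) = 1 + fρ
- understatement of the standard error: 1 − 1/√DE
- true error rate of the nominal test: 2[1 − Φ(1.96/√DE)]
- equivalent independent charts: 600/DE

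| f | ρ | DE | SE too small by | True error rate | Equivalent charts |
|---|---|---|---|---|---|
| 0 | any | 1.000 | 0% | 0.0500 | 600 |
| 2% | 0.3 | 1.006 | 0.30% | 0.0507 | 596 |
| 2% | 0.7 | 1.014 | 0.69% | 0.0516 | 592 |
| 5% | 0.3 | 1.015 | 0.74% | 0.0517 | 591 |
| 10% | 0.5 | 1.050 | 2.41% | 0.0558 | 571 |
| 20% | 0.7 | 1.140 | 6.34% | 0.0664 | 526 |

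For the last row: 1 + 0.20 × 0.7 = 1.14; 1 − 1/√1.14 = 0.063; 600/1.14 = 526.

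**Simulation.** 600 charts and seven terms (insurance, deprivation, distance, two for race/ethnicity, sex, age), with all true effects null. Logistic: 50,000 replicates per setting (Monte Carlo standard error about 0.001 per term). Cox: 20,000 replicates (about 0.0015), exponential times censored at 14 months. Completion was assumed at 71.6%, the mean of 49.5/65 and 37.5/56 from the Background; logistic was also run at 43.5%, the mean of 49.5% and 37.5%. Error rates with model-based standard errors, averaged over insurance, deprivation and distance:

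| f, ρ | Logistic (71.6%) | Logistic (43.5%) | Cox (71.6%) |
|---|---|---|---|
| 0 | 0.0506 | 0.0503 | 0.0521 |
| 2%, 0.3 | 0.0514 | 0.0513 | 0.0528 |
| 2%, 0.7 | 0.0512 | 0.0529 | 0.0529 |
| 5%, 0.3 | 0.0517 | 0.0530 | 0.0526 |
| 10%, 0.5 | 0.0567 | 0.0554 | 0.0575 |
| 20%, 0.7 | 0.0669 | 0.0670 | 0.0711 |

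Household cluster-robust standard errors gave 0.0500-0.0519 (logistic) and 0.0517-0.0541 (Cox) across the settings. Sex and age terms with model-based errors stayed at 0.0505-0.0520 (logistic) and 0.0512-0.0535 (Cox). Mean coefficients were within 0.005 of zero throughout. That siblings share race/ethnicity is an assumption; if they do not, its logistic terms sit at 0.0524 even at 20% and 0.7. A separate logistic simulation at 20% and 0.7 gave 0.067 model-based against 0.051 household-robust; the Cox simulation was not repeated.

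**The case against.** The strongest reply is that nothing in the documents shows a problem. Three conditions must hold together: siblings in the cohort, positive correlation left after adjustment, and model-based standard errors. The documents establish none of them, and silence on the variance estimator is not a decision to use the model-based one. The 6.3% sits at the top of an assumed grid: 20% of 600 charts is 60 sibling pairs, and ρ = 0.7 at 71.6% completion means that 1 − 2(0.716)(0.284)(0.3), or about 88%, of pairs share the same outcome. At 2-5% the Cox results (0.0526-0.0529) cannot be told from the sibling-free 0.0521, and part of the 0.071 is that baseline excess. The plan also expects more than 600 charts, so a loss of information may be absorbed. With up to 10 terms tested at 0.05 each, the chance of at least one false positive, if the tests were independent, is already 1 − 0.95^10, about 40%. Mileage, index value and parent characteristics survive deletion and could support a later check.

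Most of this stands. It keeps the point minor and rules out any claim that the Aim 1 analysis is unsound or underpowered. It does not remove the point. The plan limits households for the interviews but has no counterpart for Aim 1, and the direction of the error is known if the conditions hold. A larger sample may restore power but does not correct the standard errors. The surviving variables are only an imperfect proxy for a household link that the study holds for a time and then deletes.

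**Conclusion.** The concern holds as a minor improvement. Aim 1 makes no allowance for siblings. Under the assumed range (0-20% of adolescents with a sibling in the cohort, residual correlation 0.3-0.7), standard errors for insurance, deprivation and distance are 0-6.3% too small, the true error rate is 0.050-0.066 by formula, and 600 charts carry the information of 600 down to 526 for those terms. Simulation agrees, reaching 0.067 (logistic) and 0.071 (Cox, against 0.052 with no siblings) at the top of the range. If few siblings are present the effect is negligible, and it may be nil. Confidence is medium, because the sibling share and the correlation are assumptions that only the data can settle.

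**What to change.** Before addresses are deleted, assign each chart a coded, non-identifying household number. Base it on the full residence address including unit, and check it against the parent or guardian characteristics and the emergency contact's address, both already collected. Report how many households contribute more than one chart. If none do, the planned analysis stands unchanged. If any do, fit the same logistic and Cox models with household cluster-robust standard errors. This covers shared households only and makes no claim about neighbourhood clustering.

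The cost is one coded variable made during the planned GIS distance step, some record checking, and one software option. No extra data are collected. Intervals for the affected terms widen by up to √1.14 − 1, about 7%, in the assumed range. One linking variable stays in the secure network, and this new use of the addresses should be named in the waiver request.

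Matching will be imperfect: missing unit numbers can merge unrelated families, and different listed addresses can split siblings. That weakens the correction but does not undo it. With 25% of sibling pairs missed and 10% of single charts wrongly paired, the simulated error rate at 20% and 0.7 is 0.055-0.056 (logistic) and 0.058 (Cox), against 0.067 and 0.071 uncorrected.
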